Appendix B Criteria for Abnormal Changes from Baseline of Vital Signs

Parameter	Unit	Lower Criteria	Upper Criteria
Pulse	bpm	<50	>120
Systolic blood pressure	mm Hg	<85	>180
Diastolic blood pressure	mm Hg	<50	>110
Body temperature	°C	<35.6	>37.7

Appendix C Criteria for Identification of Markedly Abnormal 12-Lead ECG Parameters

Parameter	Unit	Lower Criteria	Upper Criteria
HR	bpm	<50	>120
QT-interval	msec	≤50	≥460
QTcF-interval	msec	≤50	≥500 OR
			≥30 change from baseline and
			≥450

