- 16. Has a clinically significant history of head injury, trauma, or seizures.
- 17. Has a lifetime history of major psychiatric disorder, such as major depressive disorder, bipolar disorder, or schizophrenia.

- 18. Is of any concern to the investigator regarding the safe participation of the subject in the trial or for any other reason the investigator considers the subject inappropriate for participation in the trial.
- 19. Screening ECG reveals a QT interval with Fridericia correction method (QTcF) >450 ms (men) or >470 ms (women).
- 20. Has a resting HR outside of the range of 50 to 100 beats per minute, confirmed on repeat testing within a maximum of 30 minutes, at Screening Visit or Check-in (Day -1).
- 21. Has a history of serious skin reactions (hypersensitivity) to adhesives, metals, or plastic; this criterion applies only to subjects participating in the trial of the 2 wearable digital devices.

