#### 9.2.6 12-Lead ECG

Special care must be taken for proper lead placement by qualified personnel. Skin should be clean and dry before lead placement. Subjects may need to be shaved to ensure proper lead placement. Female subjects may need to remove their bra.

Subjects should be resting in a semirecumbent position for at least 5 minutes before each ECG measurement

QT intervals with QTcF will be used to calculate QT intervals in this trial.

Before each treatment period/cohort, a predose ECG will be obtained within approximately 1 hour before dosing of TAK-418. This measurement will be used as the baseline. The principal investigator should arrange to have a trial cardiologist available as needed to review ECG tracings with abnormalities.

During each treatment period, if a subject demonstrates an increase in QTcF interval ≥40 msec compared with a predose baseline measurement, the ECG will be repeated within 5 minutes. The average value of the QTcF interval from the 2 ECGs will represent the value at that time point. If the average QTcF interval increase from Baseline for any postdose time point is ≥40 msec, the subject will continue to be monitored by repeat 12-lead ECGs every 60 minutes for at least 4 hours or until the QTcF is within 40 msec of the baseline value. If prolongation of the QTcF interval ≥40 msec persists, a consultation with a trial cardiologist may be appropriate and the sponsor should be notified.

If the QTcF interval is  $\geq$ 500 msec, the sponsor should be notified and the ECGs should be reviewed by a cardiologist. The subject should be telemetry-monitored (until the QTcF is <500 msec) or should be considered for transfer to a location where closer monitoring is available.

If the subject has unstable hemodynamics, or has any clinically significant dysrhythmias noted on telemetry, the subject should be immediately transferred to an acute care setting for definitive therapy.

If repeat ECGs are required, the clinical site will decide whether to leave the electrodes in place or mark the position of the electrodes for subsequent ECGs. To mark the position of the electrodes, 12-lead electrode sites will be marked on the skin of each subject with an ECG skin marker pen to ensure reproducible electrode placement.

[figure not shown]
The following ECG parameters will be recorded: HR, PR-interval, QRS-duration, QT-interval, QTcF-interval, and the interpretation of the ECG profile by the principal investigator.

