7.11.3 Vital Signs

Descriptive statistics (N, mean, SD, median, minimum, and maximum) will be used to summarize vital sign parameters at baseline, each post-baseline visit, and change from baseline

to each post-baseline visit. Summaries will be presented by pooled placebo and each TAK-418 dose level

Individual results of vital signs that meet Takeda's markedly abnormal criteria (see Appendix B) will be summarized and provided in the data listings. If a subject has a MAV for a particular vital sign parameter, all visits for that subject for that parameter will be listed. The number and percentage of subjects with at least 1 postdose MAV signs measurement will be summarized by pooled placebo, each TAK-418 dose level and TAK-418 overall. The mapping of the subjects who meet the MAV criteria will be listed as a table. All observations, including ones at unscheduled visits, will be included in the MAV evaluation and summaries.

All vital sign results for all subjects in the Safety Set will be listed by subject in the data listings and markedly abnormal values will be flagged.

7.11.4 12-Lead ECGs

The scheduled 12-lead ECG data will be collected according to Appendix D. The ECG parameters include heart rate, PR-interval, QRS-duration, QT-interval, and QTcF interval, and the interpretation of the ECG profile by the principal investigator.

Descriptive statistics (N, mean, SD, median, minimum, and maximum) of ECG parameters will be presented for baseline, each post-baseline visit, and changes from Baseline in quantitative ECG parameters to each post-baseline visit. Only the scheduled measurements will be included in the summary. No inferential statistics will be presented.

Individual results of quantitative ECG parameters from the 12-lead safety ECGs that meet Takeda's markedly abnormal criteria (see Appendix C) will be summarized and provided in the data listings. Shift tables will be generated to show the investigator's ECG interpretations at each postdose collection by the interpretation at Baseline.

All ECG data will be presented in the listings. ECG MAVs will be flagged in the listings.

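### SAP Appendix C gives QT and QTcF a lower limit that no valid ECG can meet, and counts an uncorrected QT of 460 msec or more without regard to heart rate or baseline

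*SAP*

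**What the plan says.** SAP 5.1 includes in the primary endpoint the number and percentage of subjects who meet the markedly abnormal ECG criteria at least once after dosing. SAP 7.11.4 makes Appendix C the rule: "Individual results of quantitative ECG parameters from the 12-lead safety ECGs that meet Takeda's markedly abnormal criteria (see Appendix C) will be summarized".

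Appendix C has three rows:

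- Heart rate: "HR bpm <50 >120".
- Uncorrected QT: "QT-interval msec ≤50 ≥460". No heart-rate or baseline condition is attached.
- QTcF: "QTcF-interval msec ≤50 ≥500", or, as the alternative upper criterion, "≥30 change from baseline and" a value of at least 450 msec.

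Elsewhere the plan works with the corrected interval. Protocol 9.2.6 states: "QT intervals with QTcF will be used to calculate QT intervals in this trial". Its repeat-ECG and monitoring rules are written in QTcF. Protocol 7.2, criterion 19, excludes on QTcF: "Screening ECG reveals a QT interval with Fridericia correction method (QTcF) >450 ms (men) or >470 ms (women". Criterion 20 covers heart rate and excludes a subject who "Has a resting HR outside of the range of 50 to 100 beats per minute", once confirmed on repeat.

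**The concern.** There are two separate faults in one table.

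First, a lower limit of 50 msec for QT and QTcF is not a value that an ECG can produce. The criterion appears two-sided but works only on the high side, so a shortened interval would never enter the primary-endpoint count, however extreme.

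Second, uncorrected QT lengthens as the heart slows. A fixed limit of 460 msec therefore corresponds to a different degree of repolarization delay at each heart rate. At slow rates that the protocol admits, it falls below the QTcF eligibility ceiling. A subject can then be counted with an unchanged QTcF, although for QTcF values under 500 msec the table's own QTcF row demands both 450 msec and a 30 msec rise. With very small dose groups, a single such subject is visible in the table.

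**Working it through.** The documents give no event rate or QTcF distribution on this point, so there is no figure of the plan's to reproduce.

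**Inputs from the documents.** Appendix C limits as above. Eligible resting heart rate 50 to 100 bpm. Eligible screening QTcF up to 450 msec (men) or 470 msec (women). Four postdose ECGs in the schedule (1, 2 and 24 hours, Day 14). Five cohorts of 6 active and 2 placebo subjects, so 10 pooled placebo.

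**Step 1: the QT limit on the QTcF scale.** Fridericia: QTcF = QT / (60/HR)^(1/3). With QT = 460 msec:

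| HR (bpm) | 50 | 52 | 55 | 60 | 64 | 80 |
|---|---|---|---|---|---|---|
| Equivalent QTcF (msec) | 432.9 | 438.6 | 446.8 | 460.0 | 470.0 | 506.3 |

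**Step 2: which eligible subjects are over it.** A subject with a given QTcF meets QT ≥460 at any rate up to HR = 60 × (QTcF/460)^3.

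- Man at QTcF 450: 60 × (450/460)^3 = 56.2 bpm. At 50 bpm his QT is 450 × (60/50)^(1/3) = 478 msec.
- Woman at QTcF 470: 60 × (470/460)^3 = 64.0 bpm. At 50 bpm her QT is 499 msec.
- QTcF 430: 49.0 bpm, so never at an eligible rate.
- QTcF 500: 77 bpm. Above that rate QT ≥460 already implies QTcF ≥500, and the QT row adds nothing.

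Below 50 bpm the heart-rate row already counts the subject. The events that only the QT row can create without QTcF prolongation therefore lie between 50 and about 56 bpm in men and 50 and about 64 bpm in women, and only in the upper part of the eligible QTcF range.

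**Step 3: an event with no change in QTcF.** Hold QTcF at 435 msec. At 60 bpm QT is 435 msec; at 50 bpm it is 435 × (60/50)^(1/3) = 462 msec. The slower rate alone creates the event, and the QTcF and heart-rate rows stay silent.

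**Step 4: the lower limit.** QT = 50 msec is 50/1200 = 4.2% of the RR interval at 50 bpm and 50/500 = 10% at 120 bpm. As QTcF it is 47 and 63 msec. No valid tracing comes near this.

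**Step 5: size, under stated assumptions.** Simulation with QTcF mean 400 to 410 msec (SD 18, limit 450), heart rate mean 64 to 60 bpm (SD 8, floor 50), within-subject SD 8 msec and 4 bpm, four postdose ECGs and no drug effect. The eligibility limits were handled in two ways.

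| | Values beyond a limit set to it | Subjects beyond a limit excluded |
|---|---|---|
| Any QT ≥460 | 2.3% to about 9% | 1.5% to 5.8% |
| Added to the any-ECG count by the QT row | 0.5% to 2.1% | 0.5% to 1.8% |

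In the first column 77% to 78% of the subjects with QT ≥460 are already counted by another row, nearly always heart rate below 50 bpm. In the second, the share is about two thirds (1 − 0.5/1.5 = 67%; 1 − 1.8/5.8 = 69%). In the first column the heart-rate row alone flags 12% to 24% of subjects.

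In 40 subjects the QT row adds 0.005 × 40 = 0.2 to 0.021 × 40 = 0.8 expected subjects. Those added whose postdose QTcF never reaches 450 msec are 0.25% to 0.95%, or 0.1 to 0.4 of 40.

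**Step 6: effect of one subject.** 1/6 = 16.7 percentage points in a dose group; 1/10 = 10 points in pooled placebo.

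**The case against.** The best defence is that little turns on this. The ECG summaries are descriptive, with no inferential statistics. Placebo subjects face the same rule. All ECG data are listed with markedly abnormal values flagged, so a reader can see heart rate, QT and QTcF for any flagged subject. Raw QT is a recorded parameter, the table is the sponsor's standard one, and using QTcF for eligibility does not forbid also reporting QT. The nonclinical signal in Protocol 6.3.2 is an effect on hERG potassium currents, and the documents raise no concern about QT shortening. All of this stands. It limits the consequence, but it does not make a limit of 50 msec usable or give the QT row a heart-rate condition.

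Three stronger readings are tempting and not supported:

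- A reader might infer that the QT row fills the ECG component with slow-heart-rate subjects. In the simulation the heart-rate row does most of that; the QT row adds about 0.5% to 2%.
- A reader might infer that detection is lost if the drug raises heart rate, as seen in monkeys at 100 mg/kg. The rows are alternatives, and the QTcF row applies at every heart rate. Above about 77 bpm the QT row is merely redundant. The documents report no heart-rate effect in humans.
- A reader might infer that the 50 was copied from the heart-rate row. The match is suggestive, but the documents cannot confirm it.

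**Conclusion.** The point holds at a modest size. The lower limits for QT and QTcF are wrong as written: the low side of the repolarization criterion cannot be met. That rests on physiology and on the share of the RR interval shown above, not on any assumed distribution. The upper QT limit lets eligible subjects with slow heart rates be counted with no QTcF rise, and some can meet it before dosing. That follows from the documents' own limits and the Fridericia formula.

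How often it would happen is an assumption, because the documents give no QTcF or heart-rate distribution: about 1.5% to 9% of subjects with any QT ≥460 msec, but only about 0.5% to 2% added to the any-ECG count. The simulation caps everyone at the male QTcF limit, so it does not cover women with QTcF between 450 and 470 msec. The 478 and 499 msec examples are extremes at exactly 50 bpm and the QTcF ceiling. The practical risk is one misleading subject in a group of 6 or 10, not a systematic distortion of the treatment comparison.

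**What to change.** Before unblinding, amend SAP Appendix C in two places.

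1. Replace the lower limits for QT and QTcF with values that can occur, set by the sponsor's cardiology function. The documents give no basis for a particular value, and none is proposed here.
2. Reconcile the QT row with the QTcF-based rules in Protocol 7.2 and 9.2.6 and in the table's own QTcF row. Base the repolarization count in the primary endpoint on the existing QTcF row, and report QT of 460 msec or more separately in the descriptive tables and listings.

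The cost is two table edits, a matching line in SAP 7.11.4, and a documented departure from the sponsor's standard table. No data are lost, because QT stays in the summaries and listings. If the sponsor prefers to keep the QT row in the count, the report should show, for each subject counted by that row alone, the heart rate and QTcF at the same reading and at baseline.

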Appendix D Schedule of Trial Procedures Schedule of Activities

	Day(s)) (a)		Scheduled Time (a)						Follow- up/ ET (b)	CCI									
	-28 to -2	-1							,	Hours								Days		
	Screen ing		Predose Day 1	0	0.25	0.5	1	1.5	2	3	4	8	12	24	36	48	72	14 (±2)	91, 93, 182, 184 (±7)	
Administrative Procedures			'																	
Informed consent	X																			
Inclusion/exclusion criteria	X	X	X																	
Medical history/ demographics	X																			
Prior and concomitant medication review		2	X						Cont	inuous	Reviev	V						X		
Clinic Procedures/Assessme	ents																			
Full physical examination	X		X (d)															X		
Neurological examination	X		X (d)											X			X	X		
Height	X																			
Weight	X		X											X				X		
BMI	X																			
Semirecumbent vital signs (HR, SBP, and DBP)	X		X (e)				X		X					X				X		
Vital signs (respiratory rate, oral [at the floor of the mouth]/tympanic temperature)	X		X (e)				X		X					X				X		
12-lead ECG	X	X	X (e)				X		X					X				X		

	Day(s)	(a)	Scheduled Time (a)										Follow- up/ET (b)	CCI					
	-28 to -2	-1		Hours														Days	
	Screen ing		Predose Day 1	0	0.25	0.5	1	1.5	2	3	4	8	12	24	36	48	72	14 (±2)	91, 93, 182, 184 (±7)
TAK-418/placebo administration				X															
C-SSRS	X		X											X		X	X	X	
BL-VAS			X				X							X					
CCI																			
AE monitoring	XX																		
Laboratory Procedures/Ass	sessments																		
Hematology	X		X											X				X	
Urinalysis	X		X											X				X	
Serum chemistry	X		X											X				X	
hCG (females)	X	X															X	X	
CCI																			
CCI	'														· · · · ·			'	
Urine/breath alcohol test (j)	X	X																	
Hepatitis screen	X																		
HIV	X																		
PK Evaluations																		 	
Blood for plasma PK			X		X	X	X	X	X	X	X	X	X	X	X	X	X		
Urine for PK (k)				X											X				

	Day(s)) (a)							Schedu	led Tin	ne (a)							Follow- up/ ET (b)	CCI
	-28 to -2	-1		Hours Days												Days			
	Screen ing		Predose Day 1	0	0.25	0.5	1	1.5	2	3	4	8	12	24	36	48	72	14 (±2)	91, 93, 182, 184 (±7)
Biomarker Evaluations																			
CCI																			
CCI																			
CCI																			
PGx Evaluations																			
Blood sample for DNA PGx (n)			X																
Blood sample for RNA PGx (o)			X											X					
Other																			
CCI																			
Confinement			X											>	ζ				

Footnotes are on the last table page.

AE=adverse event, BL-VAS=Bond-Lader Visual Analogue Scale, BMI=body mass index, C-SSRS=Columbia-Suicide Severity Rating Scale, DBP=diastolic blood pressure, ECG=electrocardiogram, ET=early termination, F-FAD=formyl-flavin adenine dinucleotide, CCI , hCG=human chorionic gonadotropin, , PBMC=peripheral blood mononuclear cell, PGx=pharmacogenomics, PK=pharmacokinetic, HIV=human immunodeficiency virus, HR=heart rate, CCI SBP=systolic blood pressure. (a) For Cohort 3, there will be a 7 day washout between Cohorts 3A and 3B, starting from TAK-418 administration on Day 1 for Cohort 3A. For Cohort 3B, all assessments on Days -1 through Day 4 will be same as Cohort 3A. (b) CCI (d) Predose physical and neurological examinations may be done within approximately 24 hours predose. (e) Vital signs and a 12-lead ECG will be performed within approximately 1 hour predose on Day 1. (f) CCI (j) A urine alcohol test may be performed at the discretion of the investigator. (k) Urine sample for TAK-418F concentrations may be collected at a dose level projected to produce therapeutic exposure at the following time intervals: Predose (spot collection), 0 to 12 hours, 12 to 24 hours, 24 to 48 hours. (I) CCI (n) Blood for DNA PGx will be collected within 60 minutes predose. (o) Blood for RNA PGx will be collected within 60 minutes predose and 24 hours postdose. (p) CCI

TAK-418-1001 Statistical Analysis Plan <yyyy-mm-dd>

ELECTRONIC SIGNATURES

Signed	by	Meaning of Signature	Server Date (dd-MMM-yyyy HH:mm 'UTC')				
PPD		Statistical Approval	12-Dec-2017 16:07 UTC				
		Clinical Pharmacology Approval	12-Dec-2017 16:37 UTC				
		Pharmacovigilance Approval	12-Dec-2017 16:51 UTC				
		Statistical Approval	12-Dec-2017 16:54 UTC				
		Clinical Approval	12-Dec-2017 20:45 UTC
